7.2. Response/Efficacy Assessments

Treatment response will be assessed by radiographic tumor evaluation every 6 weeks (±3 days) for 12 months after the first dose of LV and pembrolizumab and every 12 weeks (±7 days) thereafter and should be calculated from Cycle 1 Day 1 during treatment. Time points for radiographic examinations should be calendar based and do not depend on cycle visits. The schedule of response assessments should not be adjusted for dose delays, dose interruptions, or other reasons for changes in the timing of a patient's study activities. No additional scans or response assessments are required after the safety follow-up period, however additional scans or response assessments may be performed as part of the patient's standard of care at any time.

Spiral CT scans of chest, abdomen, and pelvis must be obtained; a CT of the neck must also be obtained if documented or suspected involvement in this region. A diagnostic quality CT is

required unless medically contraindicated. For patients unable to tolerate contrast-enhanced CT assessments, MRI imaging is acceptable. Patients must be evaluated with same imaging modality throughout the study for efficacy assessments. If any other radiographic or disease assessment examination is conducted per standard of care, the assessment information will be collected in the CRF.

The determination of antitumor activity will be based on objective response assessments made according to RECIST Version 1.1 (for primary and secondary endpoints) and iRECIST (for exploratory endpoints). Treatment decisions by the investigator will be based on iRECIST.

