#### 5.4 Data Transformations and Derivations

#### 5.4.1 General

Reported age in years will be used; if not available, age in years will be calculated with the SAS INTCK function (with method specified as "continuous") using informed consent date and birth date.

Study SGNLVA-002 Ladiratuzumab vedotin Statistical Analysis Plan Seagen, Inc. - Confidential 01-May-2024 Page 12 of 32 Study Day will be calculated as Date – First Dose Date + 1 for dates on or after the first dose date. For dates prior to the first dose date, Study Day will be calculated as Date – First Dose Date. For all calculations of Study Day, the First Dose Date will be the earliest date of treatment administration for SGN-LIV1A or pembrolizumab.

Other time variables based on two dates, e.g., Start Date and End Date, will be calculated as (End Date – Start Date + 1) (in days) unless otherwise specified in the planned analysis section.

The following unit conversion will be implemented unless otherwise specified:

$$Months = Days / 30.4375$$

$$Years = Days / 365.25$$

Unless otherwise specified, baseline values used in all analyses will be the most recent nonmissing measurement prior to the first dose of study drug.

The end-of-treatment (EOT) date will be the date the EOT visit is performed; if an EOT visit is not performed then the EOT date will be either the EOS date or 30 days after the last dose of any study drug, whichever is earlier.

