#### 5.4.3 Best Response

Primary analysis of response will be based on RECIST Version 1.1.

A patient's best response will be the best demonstrated response to date that has been confirmed. Confirmation is required for PR and CR only. Once a patient achieves a confirmed PR, only evidence of CR will potentially change the patient's confirmed best response. The patient's best response will be used in determining the ORR.

Study SGNLVA-002 Ladiratuzumab vedotin Statistical Analysis Plan Seagen, Inc. - Confidential 01-May-2024 Page 13 of 32 Per RECIST Version 1.1, a response (CR or PR) will be considered confirmed if the following disease assessment (at least 4 weeks after the initial response) still shows response (CR or PR). A patient will have a best response of SD if there is at least one SD assessment (or better) >5 weeks after the start of treatment and the patient does not qualify for CR or PR. The details of best response are provided in 0 and Appendix E.

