#### Note:

Only timepoint responses prior to new anti-cancer therapy are considered.

To classify response throughout the study, if start day of new anti-cancer therapy exists, then set B= start day of new anti-cancer therapy, otherwise B=999999.

Set A=35 days (protocol-specified minimal days for assessment of SD, the earliest day in the

Set A=35 days (protocol-specified minimal days for assessment of SD, the earliest day in the window of first scheduled assessment.).

Days A and B define the time windows for the records to be included in the best overall response assessment.

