# Best Overall Response Algorithm:

Set best overall response to CR if:

 Any record on or before study Day B has AVALC=CR and RSCONFL=Y, where AVALC is the response variable and RSCONFL is a derived variable as a flag for a confirmed responses. The algorithm of the confirmation flag is outlined below in section "Derivation Algorithm for Confirmation Flag (RSCONFL)".

Otherwise set to PR if:

Any record on or before study Day B has AVALC=PR and RSCONFL=Y.

Otherwise set to SD if:

- Any record between study Day A and B, inclusive, has AVALC=SD; or
- Any record between study Day A and B, inclusive, has AVALC=CR/PR and RSCONFL=N.

Otherwise set to PD if:

Any record on or before study Day B has AVALC=PD.

Otherwise set to NE.

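### SAP Appendix E sets the earliest day for stable disease at 35 and attributes it to the protocol's first scan window, but that window opens 39 days after first dose, and SAP 5.4.3 states a different bound.

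*SAP*

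**What the plan says.** SAP Appendix E derives best overall response from records between two days, A and B. It defines the lower one as "Set A=35 days (protocol-specified minimal days for assessment of SD" and, in the same parenthesis, explains it as the first day of the window for the first planned scan. The algorithm then assigns SD if "Any record between study Day A and B, inclusive, has AVALC=SD", or if a CR or PR flagged as not confirmed falls in the same interval. SD is tested after confirmed CR and PR, and before PD and not evaluable (NE).

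SAP 5.4.3 describes the same rule in prose and requires "at least one SD assessment (or better) >5 weeks after the start of treatment". The best-response table in SAP Appendix D also relies on a minimum SD duration but gives no number.

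On counting days, SAP 5.4.1 says "Study Day will be calculated as Date – First Dose Date + 1 for dates on or after the first dose date", so the day of first dose is Study Day 1.

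On scan timing, Protocol 7.2 schedules imaging "every 6 weeks (±3 days) for 12 months after the first dose of LV and pembrolizumab" and says that it "should be calculated from Cycle 1 Day 1 during treatment". Protocol 6.4 and SAP Section 3 give the same interval and tolerance.

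The protocol's DCR definition (9.2.3) and its RECIST summary (Appendix J) attach no minimum time to SD.

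**The concern.** A decides whether an early scan showing SD, followed by progression or by nothing usable, counts as disease control. DCR is a secondary endpoint, reported by expansion cohort and overall. A constant that does not match its stated source leaves the reader unable to tell which rule was meant. Because 5.4.3 and Appendix E differ, two programmers working from different sections could classify the same patient differently.

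Scans this early need not be deviations. Protocol 6.5 places an end-of-treatment CT 30 to 37 days after the last dose, unless one was done in the previous 4 weeks. A patient who stops after the Day 1 dose would have it on Study Days 31 to 38, and one who stops after a Day 8 dose on Study Days 38 to 45. Both ranges overlap the days between Appendix E's A and the opening of the scan window. SAP 5.4.2 adds to this by dating an SD visit at its earliest scan.

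**Working it through.** **Inputs.** First scan at 6 weeks ±3 days from Cycle 1 Day 1 (Protocol 7.2). Study Day = elapsed days + 1 (SAP 5.4.1). A = 35, applied as an inclusive study day (SAP Appendix E). More than 5 weeks from start of treatment (SAP 5.4.3). Planned N = 40 in Part D and 62 at 1.25 mg/kg in Part C (SAP 5.2).

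**Can 35 be reproduced from its description?** Opening of the window = 6 × 7 − tolerance.
- With the stated ±3 days: 42 − 3 = 39 elapsed days, or Study Day 40. This is not 35.
- With ±7 days: 42 − 7 = 35 elapsed days, or Study Day 36. Only this tolerance gives 35, and then only as elapsed days. The protocol uses ±7 days for scans after 12 months (7.2) and ±1 week for follow-up visits after treatment stops, timed from the previous scan or visit (6.6). It does not use either for the first on-treatment scan.

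**The rules on one scale.**

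| Rule | Earliest elapsed day | Earliest Study Day |
|---|---|---|
| Appendix E as coded (Study Day 35, inclusive) | 34 | 35 |
| 5.4.3, more than 35 elapsed days | 36 | 37 |
| 5.4.3, if time is counted with the +1 | 35 | 36 |
| Opening of the protocol scan window | 39 | 40 |

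The gap to the window is 39 − 35 = 4 days if A is read as elapsed days, and 40 − 35 = 5 days as the algorithm applies it. The affected scans fall on Study Days 35 to 39. Appendix E and 5.4.3 disagree on a Study Day 35 scan under either reading of 5.4.3.

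**Direction.** Take a patient whose only SD record is on Study Day 36. With A = 35 the best response is SD. With A = 40 it is PD if a later scan shows progression, or NE if there is no later scan. An earlier A only adds qualifying records, and SD is tested before PD and NE, so no patient can move the other way.

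**Size.** The change in DCR per affected patient is 1/N.
- Part D: 1/40 = 2.5 points.
- Part C at 1.25 mg/kg: 1/62 = 1.6 points.
- All parts together, planned 189 to 211: 1/189 = 0.53 to 1/211 = 0.47 points.

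The documents do not say how many patients would be affected. As an illustration only, assume 0 to 3 such patients in Part D and an underlying DCR of 27/40 = 67.5% (exact 95% CI 50.9 to 81.4). One patient gives 28/40 = 70.0% (53.5 to 83.4). Three give 30/40 = 75.0% (58.8 to 87.3).

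**What does not move.** Confirmed CR and PR are assigned without reference to A, so confirmed ORR is unchanged. DOR, PFS and OS do not use A.

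**The case against.** The strongest reply is that no protocol rule has been broken. A scan window says when to image, not when SD counts. The protocol sets neither a 35-day nor a 39-day minimum, so against the protocol text alone A = 35 is an added restriction that can only lower DCR or leave it unchanged. This stands. A reader might infer that such a patient would be PD under the protocol, or that DCR is inflated relative to the protocol; the documents support neither. The comparison holds only against the SAP's own description of A.

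A second reply is that five weeks may be deliberate. It appears in two SAP sections, and some slack below the window edge is useful because an SD visit is dated at its earliest scan: one component scan a day early would otherwise cost the patient SD status. This is a fair reason for a five-week threshold, and it means that the label rather than the number may be at fault. It is not the reason the SAP gives, and it does not reconcile the inclusive Study Day 35 with the bound in 5.4.3.

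Third, the effect needs a sole qualifying record within five study days, on a descriptive endpoint with no formal testing (SAP 5.7). That limits the weight of the point but does not remove it.

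**Conclusion.** The point holds as a mismatch within the SAP. A is 4 elapsed days, or 5 study days, earlier than its own definition implies. Its attribution to the protocol has no source there, and 5.4.3 and Appendix E give different bounds. Relative to the window-based definition, DCR can be higher but not lower, by 2.5 points per affected patient at N=40 and 1.6 at N=62.

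This rests on reading A as the study day defined in 5.4.1, as the algorithm does, and on taking the first scheduled assessment to be the 6-week on-treatment scan. The number of affected patients cannot be derived from the documents and is probably small. It would be wrong to conclude that the primary endpoint is at risk, or that 39 days is a minimum set by the protocol. This is a minor point, worth correcting because the rule decides a secondary endpoint and the correction is cheap.

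**What to change.** Set A to the lower edge of the first scan window. That is 39 days after first dose, entered as Study Day 40 because the algorithm works in study days; entering 39 would leave it one day early. Use the same bound and counting convention in 5.4.3.

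If the sponsor wants a five-week threshold, for example to allow for the dating rule in 5.4.2, delete both the attribution to the protocol and the window explanation. Then give the actual reason, say whether it means elapsed days or study days, and state one identical rule in 5.4.3 and Appendix E. Either way, reporting how many patients change category between the two cut-offs would settle the size.

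The cost is one constant and a sentence or two, made by SAP amendment before database lock or documented in the study report, as SAP Section 1 allows. The downside of Study Day 40 is that DCR may be slightly less favourable, and a visit with one component scan just before the window could lose SD status if no later record qualifies.

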# Best Overall Response Algorithm:

Set best overall response to CR if:

 Any record on or before study Day B has AVALC=CR and RSCONFL=Y, where AVALC is the response variable and RSCONFL is a derived variable as a flag for a confirmed responses. The algorithm of the confirmation flag is outlined below in section "Derivation Algorithm for Confirmation Flag (RSCONFL)".

Otherwise set to PR if:

Any record on or before study Day B has AVALC=PR and RSCONFL=Y.

Otherwise set to SD if:

- Any record between study Day A and B, inclusive, has AVALC=SD; or
- Any record between study Day A and B, inclusive, has AVALC=CR/PR and RSCONFL=N.

Otherwise set to PD if:

Any record on or before study Day B has AVALC=PD.

Otherwise set to NE.

#### Derivation Algorithm for Confirmation Flag (RSCONFL)

- For records with AVALC=CR or PR,
  - a) Set to Y if CR/PR is confirmed,
  - Set to N if the next available scan did not confirm the response (e.g. PR followed by PD).
  - Set to missing if there is no available scan to confirm the response (eg. at interim data cut)

Study SGNLVA-002 Ladiratuzumab vedotin Statistical Analysis Plan Seagen, Inc. - Confidential 01-May-2024 Page 31 of 32

- For all other records (eg. AVALC not CR or PR), leave the value for the variable RSCONFL as missing.
- Confirmation means a PR is followed by a PR or CR (ignoring two NEs or 1SD in between) at least 28 days (4 weeks) later (ie, date of second PR/CR − date of first PR ≥28), or a CR is followed by a second CR (ignoring two NEs in between) at least 28 days later. If there are 2 NEs between 2 responses, the 2 responses need to be within 3 months.
- CR followed by PR should be considered as data issue, and will not be considered a confirmed PR at the time of the previous (initial) CR.

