# APPENDIX D RECIST CRITERIA SUMMARY (VERSION 1.1)

Response Evaluation Criteria for Solid Tumors		
Term	Definition	
Complete response (CR)	Disappearance of all target lesions. Any pathological lymph nodes must have reduction in short axis to <10 mm.	
Partial response (PR)	$A \ge 30\%$ decrease in the sum of diameters of target lesions, taking as reference the baseline sum diameters.	
Progressive disease (PD)	At least a 20% increase in the sum of diameters of target lesions, taking as reference the smallest sum on study (this includes the baseline sum if that is the smallest on study). In addition to the relative increase of 20%, the sum must also demonstrate an absolute increase of at least 0.5 cm. The appearance of one or more new lesions is also considered progression.	
Stable disease (SD)	Neither sufficient shrinkage to qualify for PR nor sufficient increase to qualify for PD, taking as reference the smallest sum diameters while on study.	
Measurable lesion	Must be accurately measured in at least one dimension (longest diameter in the plane of measurement is to be recorded) with a minimum size of 10 mm by CT scan (CT slice thickness no greater than 5 mm).	

From RECIST Version 1.1 (Eisenhauer 2009)

Best overall response when confirmation of CR and PR required				
Overall response First time point	Overall response Subsequent time point	Best overall response		
CR	CR	CR		
CR	PR	SD, PD or PR a		
CR	$SD_p$	SD provided minimum criteria for SD duration met, otherwise, PD		
CR	PD	SD provided minimum criteria for SD duration met, otherwise, PD		
CR	NE	SD provided minimum criteria for SD duration met, otherwise, NE		
PR	CR	PR		
PR	PR	PR		

Study SGNLVA-002 Ladiratuzumab vedotin Statistical Analysis Plan Seagen, Inc. - Confidential 01-May-2024 Page 29 of 32

PR	$SD_p$	SD
PR	PD	SD provided minimum criteria for SD duration met, otherwise, PD
PR	NE	SD provided minimum criteria for SD duration met, otherwise, NE
NE	NE	NE

CR = complete response, PR = partial response, SD = stable disease, PD = progressive disease, and NE = inevaluable.

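### SAP Appendix E classes a lone unconfirmed PR or CR with no later scan as NE, where SAP 5.4.3 makes it SD; DCR is lowered if it is built on Appendix E

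*SAP*

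**What the plan says.** SAP Appendix E builds best overall response from a confirmation flag, RSCONFL.

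- A response with no later scan: "Set to missing if there is no available scan to confirm the response (eg. at interim data cut".
- A response with a later scan that fails to confirm it: "Set to N if the next available scan did not confirm the response (e.g. PR followed by PD".
- The CR and PR steps need the flag to be Y.
- The SD step can be entered in two ways. One is through a stable-disease record: "Any record between study Day A and B, inclusive, has AVALC=SD; or". The other is through a response that a later scan failed to confirm: "Any record between study Day A and B, inclusive, has AVALC=CR/PR and RSCONFL=N".
- PD follows if there is a PD record. Anything left over is caught by "Otherwise set to NE".

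Day A is 35 and Day B is the start of new anti-cancer therapy, if there is one.

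Two other places in the SAP cover the same ground. Section 5.4.3 states: "A patient will have a best response of SD if there is at least one SD assessment (or better) >5 weeks after the start". That rule applies when neither CR nor PR is reached, and its clock runs from first treatment. The Appendix D table, for a PR or a CR followed by an NE time point, gives: "SD provided minimum criteria for SD duration met, otherwise, NE".

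DCR (SAP 6.6.1.3) is the proportion with CR, PR or SD, reported by expansion cohort and overall.

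**The concern.** The algorithm orders patients the wrong way round. With one usable scan and nothing after it, documented shrinkage gives NE and no shrinkage gives SD. A PR followed by progression also gives SD, so the patient last seen in response ranks below the patient known to have progressed.

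At stake are DCR, a secondary endpoint reported with an exact interval, and the SD and NE rows of the best-response table. NE counts against disease control, so any such error can only lower DCR. Appendix E is also the most detailed text on the point and the one most likely to be programmed.

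**Working it through.** No printed figure in the plan depends on this rule, so the main check is a trace of the algorithm.

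**Inputs.** Day A comes from the Appendix E note: "Set A=35 days (protocol-specified minimal days for assessment of SD, the earliest day in the" first scheduled window. The first scan is due at 6 weeks ±3 days (Protocol 7.2). Its earliest on-schedule time is 42 − 3 = 39 days, so every on-schedule scan is past Day 35. The flag and step rules are those set out above.

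**Trace for a PR at Day 42 with no later scan.** The flag is missing. CR step: needs Y, fails. PR step: needs Y, fails. SD step: no SD record, and the flag is not N, fails. PD step: no PD record, fails. Result: NE.

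| Records | Flag on the response | Appendix E | SAP 5.4.3 |
|---|---|---|---|
| PR only, Day 42 | missing | NE | SD |
| CR only, Day 42 | missing | NE | SD |
| SD only, Day 42 | not applicable | SD | SD |
| PR Day 42, PD Day 84 | N | SD | SD |
| SD Day 42, PR Day 84, then none | missing | SD, from the SD record | SD |
| PR Day 42, PR Day 84 | Y | PR | PR |
| PR Day 42, NE Day 84 | N or missing, not settled | SD or NE | SD |
| PR only, Day 30 | missing | NE | NE |
| SD only, Day 30 | not applicable | NE | NE |

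The fault is therefore confined to patients with a first response on or after Day 35, no SD record from Day 35, and no later usable scan. A PR at Day 42, new therapy at Day 60 and a second PR at Day 84 also gives NE, because Appendix E ignores scans after new therapy.

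**Size per patient.** The effect on DCR is 100/N points, with N as DCR is reported:

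- Part D: 100/40 = 2.5
- Part C expansion: 100/60 = 1.7
- Part B Cohort 1: 100/48 = 2.1
- Part B Cohort 2: 100/25 = 4.0
- Overall: 100/211 = 0.47 to 100/189 = 0.53

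**Illustration for Part D.** The Clopper-Pearson limits are the 0.025 quantile of Beta(x, n−x+1) and the 0.975 quantile of Beta(x+1, n−x). For 28/40 they are 53.5% and 83.4%, which agrees within rounding with the 53% and 83% printed in SAP 5.2.4. Assume, since the documents give no count, a correct DCR of 28/40 (70.0%) and 1 to 4 affected patients. Appendix E would then report from 27/40 = 67.5% (50.9% to 81.4%) down to 24/40 = 60.0% (43.3% to 75.1%).

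**ORR.** It requires a flag of Y. SD and NE are both non-response, so ORR does not change.

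**The case against.** Section 5.4.3 already gives the sensible answer, and Appendix E is meant only to supply its details. The missing flag is illustrated by an interim cut, and Appendix E then has a pending-confirmation category for that setting. On this view the text is an interim rule with the final case left unstated. That is a fair account of how the gap probably arose. It does not close the gap: the interim cut is given as an example, no other flag value is offered for a patient with no later scan, and the pending category sits under a heading for interim data analyses. The primary analysis takes place when all treated patients are off study (SAP 5.10), when nothing is pending.

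Four further points stand and limit the concern.

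- The Appendix D row concerns a later time point assessed as NE, not the absence of any scan. It is the nearest row rather than a direct contradiction. For PR then NE, Appendix E can be read as agreeing with it.
- SAP 5.4.3 says best response is used for ORR. Section 6.6.1.3 does not say that DCR uses Appendix E.
- The group should be small. The protocol asks for a scan at least 4 weeks after a first response (Figures 1 and 2), CT at end of treatment unless done within 4 weeks, and end-of-treatment evaluations before new therapy (6.5). Any later non-confirming scan before new therapy sets the flag to N and gives SD. Death, withdrawal or deterioration without imaging remain possible routes.
- The analysis is descriptive, with no formal hypothesis testing (SAP 5.7).

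**Conclusion.** Appendix E as written gives the wrong category to a lone PR or CR from Day 35 onward that has no later scan before new therapy. It contradicts SAP 5.4.3 and is out of line with the nearest Appendix D row. Each such patient inflates the NE row and, if DCR is derived from this best response, lowers DCR by 1/N: 2.5 points in Part D, about 1.7 in the Part C expansion and about 0.5 overall.

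A reader might infer that DCR is known to be understated, or understated by some percentage of patients. The documents do not support that. They give no count of such patients, the count may be zero or small given the required scans, and the derivation of DCR from Appendix E is likely but unstated. Nor should the pooled sizes in the sample-size section (60 at the MAD, 62 at 1.25 mg/kg, 30 at 2.0 mg/kg) be used as denominators, because DCR is reported by expansion cohort and overall. Confirmed ORR, the primary efficacy endpoint, is untouched.

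**What to change.** In SAP Appendix E:

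1. For the final analysis, let the SD step accept any CR or PR record between Day A and Day B that is not confirmed, whether the flag is N or no later scan is available.
2. Keep the missing flag and the pending-confirmation category for interim data cuts only. Accepting missing as SD at every analysis would clash with the pending category.
3. State that a PR or CR followed only by NE is handled as in Appendix D: SD if the minimum duration is met.

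In SAP 6.6.1.3, state that DCR uses this best overall response.

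The cost is a few lines of SAP text and one condition in the response derivation program, with the NE-only case coded to match. No new data are needed.

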APPENDIX J: RECIST CRITERIA SUMMARY (VERSION 1.1)

Response Evaluation Criteria in Solid Tumors

Term	Definition
Complete response (CR)	Disappearance of all target lesions. Any pathological lymph nodes must have reduction in short axis to <10 mm.
Partial response (PR)	$A \ge 30\%$ decrease in the sum of diameters of target lesions, taking as reference the baseline sum diameters.
Progressive disease (PD)	At least a 20% increase in the sum of diameters of target lesions, taking as reference the smallest sum on study (this includes the baseline sum if that is the smallest on study). In addition to the relative increase of 20%, the sum must also demonstrate an absolute increase of at least 0.5 cm. The appearance of one or more new lesions is also considered progression.
Stable disease (SD)	Neither sufficient shrinkage to qualify for PR nor sufficient increase to qualify for PD, taking as reference the smallest sum diameters while on study.
Measurable lesion	Must be accurately measured in at least one dimension (longest diameter in the plane of measurement is to be recorded) with a minimum size of 10 mm by CT scan (CT slice thickness no greater than 5 mm).

From RECIST Version 1.1 (Eisenhauer 2009)

A response (CR or PR) will be considered confirmed if the following disease assessment (at least 4 weeks after the initial response) still shows response (CR or PR). In cases where the initial response is followed by SD, it will be considered as confirmed if the SD is later followed by PR or CR. For example, if a patient had PR in week 8, SD in week 12, and PR in week 16, this PR will be considered as confirmed.

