# Appendix E RECIST Response Confirmation Algorithm Details

A response (CR or PR) will be considered confirmed (RSCONFL=Y) if the following disease assessment (at least 4 weeks after the initial response) still shows response (CR or PR).

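### For a CR followed by a PR with no later confirming response, the SAP's confirmation-flag derivation contradicts protocol Appendix J, SAP 5.4.3 and the opening of its own appendix, so the same scans can be responder or non-responder in the primary ORR

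*SAP*

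**What the plan says.** **Texts that confirm CR then PR.** Protocol Appendix J treats a response as confirmed "if the following disease assessment (at least 4 weeks after the initial response) still shows response (CR or PR"). SAP 5.4.3 repeats the condition ("at least 4 weeks after the initial response) still shows response (CR or PR")). The opening sentence of SAP Appendix E does the same and attaches the flag: such a response "will be considered confirmed (RSCONFL=Y").

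**Text that does not.** The RSCONFL derivation later in SAP Appendix E confirms a PR by a later PR or CR, but a CR only by a second CR. On the mixed case it says "CR followed by PR should be considered as data issue, and will not be considered a confirmed PR". The sentence goes on to limit itself: the pair "will not be considered a confirmed PR at the time of the previous (initial) CR".

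**Text that depends on the case.** The best-response table in SAP Appendix D gives SD, PD or PR for CR then PR. Note a explains why. If the CR call was mistaken, it is changed to PR and the best response is PR. If the CR was real, the later time point is progression, and the best response depends on whether the minimum SD duration was met.

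**Intervening SD.** Protocol Appendix J and note b of SAP Appendix D accept a response followed by SD and then by PR or CR. The RSCONFL derivation ignores one SD only when the first response is a PR.

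**Two NEs.** The derivation ignores two NEs between responses but adds: "If there are 2 NEs between 2 responses, the 2 responses need to be within 3 months".

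**The concern.** SAP 5.4.3 makes best response the input to ORR, and the best-response algorithm in Appendix E turns an unconfirmed CR or PR from Day 35 onward into SD. The confirmation rule therefore decides who is a responder in the primary analysis. The trial is open label and investigator assessed, with cohorts of about 30 to 62 patients. An unsettled rule leaves the choice to whoever programs the flag, possibly after the affected patients can be identified. SAP section 8.2 lists changes, but neither the CR-then-PR rule nor any other departure from Appendix J on confirmation is among them.

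**Working it through.** **1. Reproduce the plan's figures.** Clopper-Pearson limits for Part D (N=40) with 20, 24 and 28 responders are 33.8–66.2%, 43.3–75.1% and 53.5–83.4%. For Part C (N=62) with 31, 37 and 43 they are 37.0–63.0%, 46.4–71.9% and 56.3–80.4%. Both match the tables in protocol 9.1 and SAP 5.2.

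**2. Run the same scans through each text.** Scans are 6 weeks apart, with the first response at Day 42, which is past the Day 35 minimum for SD.

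| Sequence | Protocol App. J | SAP App. E derivation and algorithm | SAP App. D notes |
|---|---|---|---|
| CR, PR, PD | responder | SD | PR if the CR is corrected; otherwise non-responder |
| CR, PR, no later scan | responder | SD | as above |
| CR, PR, PR | responder from scan 1 | PR, from scan 2 | PR from scan 1 if the CR is corrected; if the CR stands, scan 2 is PD |
| CR, SD, CR | responder | SD | responder (note b) |

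For the first three rows, SAP 5.4.3 and the opening of Appendix E agree with Appendix J. Neither states a rule for an intervening SD.

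In row 3 the patient remains a responder under Appendix E. The response start moves from scan 1 to scan 2, so DOR is shorter by 6 × 7 = 42 days (42 / 30.4375 = 1.4 months).

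**3. Size per affected patient.**
- Part D: 1/40 = 2.5 points. For example, 24/40 = 60.0% (43.3–75.1%) against 23/40 = 57.5% (40.9–73.0%).
- Part C at 1.25 mg/kg: 1/62 = 1.6 points. For example, 37/62 = 59.7% (46.4–71.9%) against 36/62 = 58.1% (44.8–70.5%).
- 2.0 mg/kg: 1/30 = 3.3 points.

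The documents give no count of affected patients. If 1 to 3 are assumed, the shift is 2.5 to 7.5 points in Part D and 1.6 to 4.8 points in Part C.

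**4. Two-NE limit against the scan schedule.** By the SAP's conversion, 3 months = 3 × 30.4375 = 91.3 days. Response, NE, NE, response spans three intervals:
- 6-weekly scans: 3 × 42 = 126 days (120–132 with ±3-day windows).
- 12-weekly scans: 3 × 84 = 252 days (238 at the earliest).
- Across the change of interval: 42 + 42 + 84 = 168, or 42 + 84 + 84 = 210 days.

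All exceed 91.3 days. The exception comes from the extra confirmation scan that protocol 3.1 permits at least 4 weeks after a first response. Response, NE at +28, NE at +42 and response at +84 days (78–90 with windows) meets the limit in the first year. In the 12-weekly phase the same pattern takes 168 days and fails.

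**The case against.** The strongest defence is that Appendix E is the operative specification. SAP 5.4.3 sends the reader there for detail, and protocol 9.3 describes its own statistical text as a summary of the SAP. That would settle the matter if Appendix E were consistent. It is not: its opening sentence confirms CR then PR, and its derivation does not. No order of precedence is given.

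A second defence is that Appendices D and E can be read together. If the CR is queried as a data issue and corrected to PR, the pair becomes PR then PR, which the derivation confirms. If the CR stands, both appendices give a non-responder. This has force and points to a sensible rule. It leaves the conflict with protocol Appendix J, SAP 5.4.3 and the opening of Appendix E untouched.

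Two stronger readings are tempting, and the documents do not support them.

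- A reader might infer that every patient with CR then PR is lost from ORR. The derivation sentence applies only at the time of the initial CR. The algorithm accepts any later PR that is itself confirmed, so CR, PR, PR and CR, PR, CR both give PR.
- A reader might infer that the 3-month limit can never be met and removes responders whom the protocol would count. An extra scan at about 4 weeks meets it in the first year. Appendix J has no NE allowance at all, so the SAP's allowance goes beyond the protocol and its cap takes away no protocol-defined responder.

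It is also fair that ORR is descriptive, with no hypothesis test.

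**Conclusion.** The inconsistency is real and reaches the primary endpoint, but only for CR then PR without a later confirming response and for CR, SD, CR. In the first case, protocol Appendix J, SAP 5.4.3 and the opening of Appendix E give a responder, while the Appendix E derivation gives SD. In the second, Appendix J and note b give a responder and the derivation gives SD. Each such patient is worth 2.5 points at N=40, 1.6 at N=62 and 3.3 at N=30. For CR, PR, PR the Appendix E effect is confined to the response date and hence DOR, although note a with a standing CR would make the second scan progression.

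The conclusion assumes that scans follow the schedule, that the first response falls on or after Day 35, and that the texts are applied as written. The number of affected patients cannot be derived from the documents and is probably small. The two-NE limit is a secondary matter of fit with the scan schedule and does not conflict with Appendix J.

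**What to change.** Before database lock, choose one rule and state it identically in SAP 5.4.3, Appendix D and Appendix E. List any departure from protocol Appendix J in SAP section 8.

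One workable rule is Appendix D note a. Query the CR. If it is corrected to PR, the pair is a confirmed PR dated at the first time point. If the CR stands, the later time point is PD. That last branch differs from Appendix J and would need to be declared.

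Deleting the data-issue bullet alone is not enough, because the preceding bullet still requires a CR to be followed by a second CR. Both bullets need amending, as do the looser sentences in 5.4.3 and at the start of Appendix E. Align CR, SD, CR in the same edit.

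For the two-NE allowance, either express the limit in scheduled scan intervals with their windows, or state that it applies only when an extra confirmation scan was done. How long a gap to tolerate is the sponsor's choice.

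The cost is a SAP edit and a small change to the flag program. Under protocol 9.3, an analysis change needs a protocol amendment only if site conduct changes, and this one does not alter it. If lock has already passed, document the rule applied and the patients affected in the clinical study report.
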